1.0 Administrative Information

1.1 Trial title and registration

Million Veteran Program Return of Actionable Results - Familial Hypercholesterolemia (MVP-ROAR-FH) Study. ClinicalTrials.gov Identifier: NCT04178122

1.2 Revision history

| SAP version | Section changed | Description | Date amended |
|-------------|-----------------|--------------|--------------|
| 1.0 | | Date created | 09/19/2023 |

1.3 Key personnel

1.3.1 Principal investigator

The principal investigator (PI) supervises all aspects of the study. The PI takes responsibility for the scientific development and conduct of the study, including meeting study goals and timelines, monitoring participant safety, and oversight of the dissemination of research findings.

1.3.2 Biostatistician

The biostatistician advises the study team on the appropriate study design and statistical analysis of study outcomes. The biostatistician conducts and/or reviews sample size and power calculations and provides supervision to the data analyst in performing data collection, data cleaning, and statistical analysis of study data.

1.3.3 Data manager/analyst

The data manager creates and maintains the database housing study data. The data analyst ensures the capture of study data and performs requisite merging and cleaning of study data. The data manager prepares summary data tables for study planning, reporting, monitoring, and dissemination of results. The data manager prepares and maintains participant randomization tables and mechanisms for treatment allocation. The data manager does not engage in the enrollment or allocation of participants to study treatments. Under the direction of the biostatistician, the data analyst may perform statistical analysis of study outcomes.

1.3.4 Research genetic counselor / project manager

The research genetic counselor / project manager is responsible for the day-to-day operations of the MVP-ROAR-FH Study. They also obtain participant consent for study participation and genetic confirmation testing and deliver the intervention to enrolled participants.

2.0 Introduction

This document details the proposed data analysis, presentation, and reporting of outcomes associated with the MVP-ROAR-FH Study. The results reported in the primary study

manuscript(s) will adhere to the strategy outlined here. All amendments to this plan will be documented and reviewed by the relevant key personnel listed within this document. Any deviations to this plan will be justified and detailed in the final manuscript(s). Further analysis, including subset and exploratory analyses not included here, may occur as needed and will be justified and described if reported. This document follows the published guidelines for the content of statistical analysis plans in clinical trials.¹

2.1 Background

Familial hypercholesterolemia (FH) is a genetic disorder characterized by elevated low-density lipoprotein cholesterol (LDL-C) levels and increased risk for cardiovascular disease. The MVP-ROAR-FH study aims to return potentially actionable genetic results associated with FH to Million Veteran Program (MVP) participants and their primary care providers. Informing participants of this information might lead to earlier interventions and improved health outcomes.

2.2 Study objectives

The primary objective of MVP-ROAR-FH is to evaluate the difference in change in LDL-C (end-of-study LDL-C minus baseline LDL-C) after 6 months between the Immediate Results arm and the Delayed Results arm. Secondary and exploratory objectives include an assessment of the difference in the proportions of participants reaching LDL-C targets between arms, examination of the difference in the intensification of lipid-lowering pharmacotherapy between arms, and evaluation of medication adherence, cascade testing, lifestyle behaviors, healthcare costs, and quality-of-life after a 6-month observation period.

2.3 Primary outcome and research hypothesis

Primary outcome: Change in LDL-C 6 months after randomization

Null hypothesis: 6-month change in LDL-C is not significantly different between groups receiving their genetic results at baseline compared to those receiving their results after 6 months.

Alternative hypothesis: 6-month change in LDL-C is significantly different between groups receiving their genetic results at baseline compared to those receiving their results after 6 months.

3.0 Trial Methods

3.1 Trial design

The MVP-ROAR-FH Study is a randomized controlled trial (RCT). MVP participants suspected of carrying a genetic variant associated with familial hypercholesterolemia are recontacted, enrolled, and, upon receipt of a DNA sample, randomly assigned either to an Immediate Results arm, where the return of genetic results intervention occurs at baseline, or a Delayed Results arm, where the intervention is delivered at the end of the study, after 6 months. The intervention consists of variant confirmation testing and reporting, standard genetic counseling, provision of informational resources to the participant and their primary care providers (PCPs), and documentation of the intervention in the medical record.

3.2 Sample size

The MVP-ROAR-FH Study aims to enroll ten participants into a pilot trial and 244 participants into the RCT.

Sample size is based on the primary outcome of change in LDL-C in each arm after 6 months. Assuming a mean LDL-C reduction of 20% in the Immediate Results arm, a mean LDL-C reduction of 0% in the Delayed Results arm, and a common standard deviation of 30%,² 72 total participants (36 per arm) are needed to have 80% power to detect a significant between-group difference at alpha=0.05. Enrollment of twice this number (144 total) will account for an absence of therapy escalation in up to 50% of participants in the Immediate Results arm. Enrollment of 180 total participants will account for up to 20% loss to follow-up.

| Change in LDL-C at 6 months | | | Total sample size required |
|-----------------------------|-----------------|-----------|----------------------------|
| Immediate Results | Delayed Results | Common SD | |
| -20% | 0% | 30% | 72 |
| -20% | 0% | 40% | 126 |
| -20% | -5% | 30% | 126 |
| -20% | -5% | 40% | 224 |

An important secondary outcome is the proportion of participants in each arm meeting accepted LDL-C targets at 6 months (<100 mg/dL for primary prevention and <70 mg/dL for secondary prevention). In preparatory-to-research analyses, only 175/322 (46%) MVP participants with a potentially pathogenic LDLR variant had a most recent LDL-C <100mg/dL. To have 80% power to detect a between-arm difference of 20% of participants meeting this LDL-C target at alpha=0.05, up to 194 total participants are needed (97 per arm). To account for up to 20% loss to follow-up, a total of 244 participants (122 per arm) are needed.

| Proportion of participants with LDL-C < 100mg/dL at 6 months | | Total sample size required |
|--|-----------------|----------------------------|
| Immediate Results | Delayed Results | |
| 10% | 30% | 124 |
| 20% | 40% | 162 |
| 30% | 50% | 186 |
| 40% | 60% | 194 |

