5.0 Statistical Considerations

5.1 Statistical framework

The principal analysis uses an intention-to-treat (ITT)¹⁵ approach to compare the Immediate Results and Delayed Results arms. Using an independent t-test, analysis of the primary outcome uses a t-statistic, and two-sided type I error rate of 0.05 to test the null hypothesis of no difference in LDL-C change between arms. To quantify the treatment arm difference for the primary endpoint, a mean difference will be presented with a corresponding confidence interval estimate. Mean change in LDL-C is also reported separately for each arm. Similarly, for secondary and other pre-specified outcomes an ITT approach is used to make outcomes comparisons across treatment groups. Subset analyses, including sensitivity and group analyses by demographic, variant confirmation status, or other study or patient characteristics, are considered exploratory and will be described in detail if reported.

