6.0 Outcome definitions and timing

6.1 Primary outcome (6-month difference in LDL-C)

Baseline (at enrollment) and end-of-study (at 6 months) LDL-C values are defined as the LDL-C measurements obtained from study-related blood draws as processed by the study's centralized laboratory. For participants for whom it is not feasible to visit their local VA facility for a blood draw at baseline, a documented LDL-C value in their medical record may be used for a study measurement, provided it is not older than 6 months from their date of enrollment and a change in lipid-lowering therapy has not occurred between the clinical LDL-C value and study enrollment. For participants for whom it is not feasible to visit their local VA facility for an end-of-study blood draw, a documented LDL-C value in their medical record may be used for a study measurement. The documented LDL-C value closest to the date 6 months after the date of randomization will be used for the end-of-study value. If no 6-month value is available, the study may use an LDL-C value obtained from the medical record during the 6-month observation period, including carry forward of the baseline value.

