7.2 Primary outcome

The difference in LDL-C reduction after 6 months between the Immediate Results arm and the Delayed Results arm will be assessed. The LDL-C values at baseline and 6 months will first be summarized descriptively for each arm. The change in LDL-C from baseline to 6 months will be calculated for each participant. An independent *t*-test will be employed to compare the mean LDL-C change between the two arms, assuming normally distributed data. If the change scores do not follow a normal distribution, a non-parametric alternative, the Wilcoxon rank-sum test, may be used. The effect size (Cohen's *d*), confidence intervals, and *P* value will be reported to determine the statistical significance of the observed difference. Additionally, potential confounders may be included in regression modeling to ensure the robustness of findings.

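### Sample size and power are stated for percent change in LDL-C, but the primary test is on absolute change, so the stated 80% is not the power of the planned test

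*SAP*

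**What the plan says.** **Planning scale.** SAP Section 3.2 says the sample size rests on the primary outcome, but every input is a percentage: "Assuming a mean LDL-C reduction of 20% in the Immediate Results arm, a mean LDL-C reduction of 0% in the Delayed Results arm", with a common SD of 30%. This gives 72 in total (36 per arm) for 80% power at alpha 0.05. The other three table rows are also in percent (mean changes of -20% against 0% or -5%, SD 30% or 40%) and give 126, 126 and 224. The 72 is doubled to 144 and then raised to 180 for 20% loss. The enrolment target of 244 comes from the secondary outcome, the proportion meeting LDL-C targets (194 evaluable before 20% loss).

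**Analysis scale.** Section 2.2 defines change as "end-of-study LDL-C minus baseline LDL-C". Section 2.3 has "Primary outcome: Change in LDL-C 6 months after randomization". The heading of Section 6.1 speaks of a 6-month difference. Section 7.2 says "The change in LDL-C from baseline to 6 months will be calculated for each participant" and uses an independent t-test "to compare the mean LDL-C change between the two arms, assuming normally distributed data". Section 5.1 sets a "two-sided type I error rate of 0.05 to test the null hypothesis of no difference in LDL-C change between arms" and reports a mean difference with a confidence interval.

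Nowhere does the SAP define the primary outcome as percent change. It gives no mean baseline LDL-C, no target difference in mg/dL and no SD of change in mg/dL.

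**The concern.** A t-test on percent change and a t-test on absolute change are different tests with different standardized effects. They coincide when every participant has the same baseline LDL-C, or under some particular relation between baseline and response that the SAP does not state. The 80% in Section 3.2 therefore describes a test that Sections 5.1 and 7.2 do not run.

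Two practical consequences follow. The trial will report a mean difference in LDL-C units, while the only effect it was designed to detect is a percentage, so the confidence interval cannot be compared directly with the design effect. And a plan that sizes on one scale and analyses on the other leaves room to argue afterwards that percent change was the intended outcome. With one primary test at 0.05, the analysed variable should be beyond dispute.

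**Working it through.** **1. Reproduce the SAP's figures on its own scale.** Inputs from Sections 3.2, 3.3 and 5.1: two-sided alpha 0.05, power 80%, 1:1 allocation. Per arm, n = 2(1.960 + 0.842)² × (SD/difference)².

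| Difference | SD | n per arm | Total | SAP |
|---|---|---|---|---|
| 20 | 30 | 35.3 → 36 | 72 | 72 |
| 20 | 40 | 62.8 → 63 | 126 | 126 |
| 15 | 30 | 62.8 → 63 | 126 | 126 |
| 15 | 40 | 111.6 → 112 | 224 | 224 |

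All four rows agree. The noncentral t gives 74 for the first row. Power at 36 per arm is 80.7% (normal) or 79.7% (t).

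**2. Move to the scale that is tested.** The SAP does not give the inputs, so assumptions are needed. Let baseline have mean 1 (an arbitrary unit) and coefficient of variation c, assumed to be 0.25 to 0.45. Keep mean percent changes of -20% and 0% and a percent-change SD of 30%. The mean difference in absolute change is then 0.20, and d = 0.20/SD, where SD² is the average of the two arm variances.

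*Model A: percent change independent of baseline.*
- Delayed variance = 0.09(1 + c²).
- Immediate variance = 0.09(1 + c²) + 0.04c².
- Example, c = 0.25: variances 0.0956 and 0.0981, SD 0.311, d = 0.20/0.311 = 0.643.

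*Model B: additive follow-up variation with constant SD s in mg/dL, lognormal baseline.*
- Percent change has SD s(1 + c²)^1.5, so an SD of 0.30 requires s = 0.30/(1 + c²)^1.5.
- Delayed variance = s²; Immediate variance = s² + 0.04c².
- Example, c = 0.25: s = 0.274, SD 0.276, d = 0.20/0.276 = 0.724.

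| c | A: d | A: power at 36 per arm (t) | A: total for 80% (t) | B: d | B: power at 36 per arm (t) |
|---|---|---|---|---|---|
| 0.25 | 0.643 | 76.7% | 80 | 0.724 | 85.8% |
| 0.35 | 0.622 | 73.9% | 84 | 0.778 | 90.2% |
| 0.45 | 0.597 | 70.5% | 92 | 0.847 | 94.3% |

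By the normal approximation, Model A gives 77.8%, 75.1% and 71.7%. The two models lie on opposite sides of the stated 80%.

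**3. Leave the mg/dL inputs free.** With an assumed mean baseline of 100 to 160 mg/dL (so that 20% is 20 to 32 mg/dL) and an assumed SD of change of 30 to 60 mg/dL, t-test power at 36 per arm runs from 29% (20 mg/dL, SD 60) to 99% (32 mg/dL, SD 30).

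**4. Check against planned enrolment.** Section 3.2 plans 97 evaluable per arm. For the full 20% effect, Model A gives t-test power of 99.4%, 99.1% and 98.5% at c = 0.25, 0.35 and 0.45. Alternatively, take the SAP's own inflation steps as given: 80 to 92 becomes 160 to 184 after doubling, and 200 to 230 after dividing by 0.8. Both are below 244.

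**The case against.** The strongest reply is that nothing in the conduct of the trial turns on this. The figure 72 is only the first step in Section 3.2. The enrolment target is 244, and Model A's effective SD of about 31 to 34% of mean baseline is smaller than the 40% SD the SAP already tabulates for the same effect (126 in total). Section 7.2 also summarises LDL-C at both times by arm, so an approximate percent comparison could be made. All of this stands, and it keeps the point to one of consistency.

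A reader might infer that spread in baseline LDL-C necessarily inflates the SD of absolute change, so that true power is below 80%. The document does not support that. It follows under Model A but reverses under Model B, and the SAP gives nothing with which to choose between them. A reader might also infer an arithmetic error, but all four totals reproduce.

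The reply does not remove the mismatch itself. Section 3.2 attributes a power to the primary outcome that was calculated for a different variable, and no section links the two scales. An approximate comparison of arm means is also not a substitute for a confidence interval on the design scale.

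**Conclusion.** The inconsistency is real and should be corrected. The 80% power at 72 participants is correct for percent change and is not the power of the t-test on end-of-study minus baseline LDL-C. How far off it is, and in which direction, cannot be determined from the SAP. The ranges of about 70 to 77% and about 86 to 94% each rest on an assumed baseline coefficient of variation of 0.25 to 0.45 and on the model named.

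It would be wrong to conclude that the mismatch leaves the trial underpowered. For the full 20% effect, 97 evaluable per arm retain about 98.5 to 99.4% power under the less favourable of the two models. That reassurance covers the full 20% effect only. It does not extend to smaller effects, such as one diluted by participants whose therapy is not escalated, which is a separate question.

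**What to change.** Keep N and put planning and analysis on one scale.

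**Preferred.** Make the primary analysis a linear model of log LDL-C at 6 months on arm and log baseline LDL-C. Report the ratio of geometric means, with its confidence interval, as a percent difference. Restate the planning inputs on that scale: the target ratio and the residual SD of log LDL-C, which the SAP does not now give. Baseline LDL-C is already collected, and adjusting for it can improve precision. The cost is more than a change of wording: the model replaces the unadjusted t-test in Sections 5.1 and 7.2 and the statement in Section 7.1 that no covariate adjustment is prespecified. The outcome definition in Sections 2.2 and 2.3 must be aligned with it.

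**Otherwise.** Keep absolute change as the primary outcome, state its unit, and restate effect, SD and power in mg/dL from available baseline data. Section 3.2 reports only a proportion below 100 mg/dL from the preparatory data, so the study team must confirm that a mean and SD can be obtained there. An SD of 6-month change needs its own source or a stated range. This changes Section 3.2 only, and the stated power may move either way.

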4.4 Analysis populations

4.4.1 Intention-to-treat populations

Intention-to-treat (ITT) populations include all patients who undergo randomization and are characterized by the treatment they were randomized to receive (Immediate Results vs. Delayed Results).

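### Doubling 72 to 144 does not protect the ITT primary comparison against 50% non-escalation: if non-escalators do not change, power at 144 evaluable is about 51%, not 80%

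*SAP*

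**What the plan says.** SAP section 3.2 opens the calculation with "Sample size is based on the primary outcome of change in LDL-C in each arm after 6 months". Its first input is "Assuming a mean LDL-C reduction of 20% in the Immediate Results arm". The comparator is set at no change, and both arms share an SD of 30%. These give 72 in total (36 per arm) for 80% power at alpha 0.05.

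Two allowances follow. The first is for non-escalation in the Immediate Results arm: "Enrollment of twice this number (144 total) will account for an absence of therapy escalation in up to 50% of participants". The second is for attrition: "Enrollment of 180 total participants will account for up to 20% loss to follow-up".

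The RCT target of 244 comes from a separate calculation in the same section, for the secondary outcome of meeting LDL-C targets. The SAP gives no primary-outcome power at 244.

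The analysis is defined elsewhere. Section 4.4.1: "Intention-to-treat (ITT) populations include all patients who undergo randomization and are characterized by the treatment they were randomized to receive". Section 5.1 makes ITT the principal approach, with an independent t-test at two-sided 0.05. Section 7.2 uses that test to "compare the mean LDL-C change between the two arms".

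**The concern.** Dropout and non-escalation affect power in different ways. Participants who drop out reduce the number analysed and leave the expected difference as it was, so dividing by the retained fraction is correct. Under ITT, non-escalators remain in the analysis and shrink the arm mean. Sample size varies with the inverse square of the difference, so halving the difference calls for four times the sample. The SAP applies the dropout correction, a factor of 1/(1 − 0.5) = 2, to what is a dilution problem, where the factor is 1/(1 − 0.5)² = 4.

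This sentence is the SAP's only statement of primary-outcome power under non-escalation. If the trial finds no significant difference, a reader relying on it would believe that up to half the Immediate Results arm could go without escalation and 80% power would still hold.

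**Working it through.** **Inputs from the SAP.** Means −20% and 0%, SD 30%, 80% power, alpha 0.05, non-escalation up to 50%, loss 20%, target 244 (section 3.2); 1:1 allocation (section 3.3); two-sided independent t-test under ITT (sections 4.4.1, 5.1, 7.2).

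**Assumptions that the SAP does not state.** (a) The 20% reduction applies to participants whose therapy is escalated. (b) Non-escalators change by 0%, like the Delayed Results arm; this is varied below. (c) The SD stays at 30 in both arms.

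**Step 1: reproduce the plan's figures.** n per arm = 2 × (1.960 + 0.842)² × (SD/difference)².

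- Difference 20, SD 30: 35.3, so 36 per arm and 72 in total, as stated. The other three table rows (126, 126, 224) also reproduce.
- Attrition: 144/0.8 = 180, as stated.

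**Step 2: dilute the effect.** With non-escalation share f and a fall of e points in non-escalators, the ITT difference is 20(1 − f) + e·f. At f = 0.5 and e = 0 it is 10 points.

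- The same formula at 10 points gives 141.3, so 142 per arm and 284 in total. The noncentral t gives 143 per arm, 286 in total.
- 284/0.8 = 355 and 286/0.8 = 357.5, so 355–358 enrolled if 20% are lost.

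**Step 3: power at the sample sizes in the SAP** (noncentral t, SD 30). The 72 per arm is 144 evaluable, which is also what 180 enrolled leaves after 20% loss. The 97 per arm is 244 enrolled with 20% loss (122 × 0.8 = 97.6). The 122 per arm is 244 with no loss.

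| Scenario | Difference | 72 per arm | 97 per arm |
|---|---|---|---|
| f = 50%, e = 0 | 10 | 51.1% | 63.7% |
| f = 50%, e = 2 | 11 | 58.9% | 71.9% |
| f = 50%, e = 4 | 12 | 66.4% | 79.2% |
| f = 50%, e = 5 | 12.5 | 70.0% | 82.3% |
| f = 50%, e = 8 | 14 | 79.4% | 89.9% |
| f = 40%, e = 0 | 12 | 66.4% | 79.2% |
| f = 30%, e = 0 | 14 | 79.4% | 89.9% |
| f = 20%, e = 0 | 16 | 88.8% | 95.9% |

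At 122 per arm, power is 73.7% for f = 50%, e = 0.

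**Step 4: where 80% power is reached.** The maximum f with e = 0 is 1 − difference/20. The break-even e at f = 50% is 2 × (difference − 10). Both use the unrounded difference.

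| Per arm | Detectable difference | Maximum f (e = 0) | Break-even e (f = 50%) |
|---|---|---|---|
| 72 | 14.1 | 29.5% | 8.2 points |
| 97 | 12.1 | 39.4% | 4.3 points |
| 122 | 10.8 | 46.0% | 1.6 points |

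**Step 5: sensitivity to the SD.** If 30 is the SD within escalators and within non-escalators, a 50/50 mixture of means −20 and 0 has SD √(900 + 0.25 × 400) = 31.6 in the Immediate Results arm. Power is then about 49% at 72 per arm, 61% at 97 and 71% at 122. A simulation of 40,000 trials gave 49.0% at 72 per arm and 61.3% at 97.

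**The case against.** **The 20% may be the mean of the whole arm.** The SAP's wording is an arm-level mean, and read literally it is already the ITT contrast. In that case 72 is enough and power is understated. This reading does not rescue the sentence, because a separate allowance for non-escalation would then have nothing to correct.

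**Zero change in every non-escalator is pessimistic, and 50% is a ceiling.** The intervention includes genetic counselling and information for participants and primary care providers (section 3.1). Adherence or lifestyle could improve without escalation. This stands as a reason to show a range. Even so, 144 evaluable reaches 80% power only if non-escalators fall by about 8 points while the Delayed Results arm falls by none, and the SAP nowhere assumes that.

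**The trial plans 244, not 144 or 180.** This softens the point considerably. At 97 per arm, power is 90% with 30% non-escalation, or 82% with 50% non-escalation and a 5-point fall in non-escalators. At 122 per arm a fall of about 1.6 points is enough. The full 50% with no change in non-escalators is still not covered, at 64% to 74%.

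**The SD could go either way.** Mixing raises it, as in step 5. If non-escalators vary less, power is higher: an illustrative SD of 20 in them gives about 55% at 144. Neither comes near 80%.

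**The consequence is limited.** The estimator, test, alpha and target are unaffected, and sections 5.1, 5.4 and 7.2 require a confidence interval and effect size, which would show any imprecision. That is true, but the power statement would still be wrong.

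**Conclusion.** The concern holds. The products 72 × 2 and 144/0.8 are right, but the factor of 2 does not match the ITT analysis. If the 20% describes escalators and non-escalators do not change, 50% non-escalation requires 284–286 evaluable, about twice the 144 stated. The protection claimed at 144 evaluable reaches only to about 29% non-escalation. The larger enrolment set by the secondary outcome extends it to about 39% after 20% loss and 46% with none. These figures rest on assumptions (a) to (c). If 20% is the whole-arm mean, the sentence is wrong in a different way, since the allowance is redundant. The sentence is correct only if non-escalators fall by about 8 points, which is not stated. This should be fixed, because it misstates the power of the primary comparison.

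**What to change.** In SAP section 3.2, replace the doubling sentence and the 180 that follows from it with a diluted-effect calculation that states:

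1. whether the 20% reduction refers to escalators or to the whole Immediate Results arm, that non-escalators stay in that arm under ITT, and the change assumed in them;
2. that with 0% change in them, 50% non-escalation gives a 10-point difference and 284–286 evaluable participants are needed for 80% power;
3. the resulting primary power in that scenario: about 51% at 144 evaluable, and at 244 enrolled about 64% with 20% loss or 74% with none;
4. the largest non-escalation share at which 80% power holds: about 29% at 144 evaluable and 39% at 97 per arm.

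If the investigators mean the 20% as a whole-arm mean, they should say so and delete the allowance. If they expect some fall in non-escalators, they should state it and recompute items 2 to 4.

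The cost is SAP wording only, with no added enrolment and no change to the test or population. The downside is a less favourable stated power for the primary outcome.

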5.4 Confidence intervals, *P* values, and multiple testing

All statistical testing is reported with an effect, a two-sided 95% confidence interval, and *P* value, unless otherwise specified. *P* values less than 0.05 will be reported as significant for the primary outcome. *P* values reported as significant for secondary outcomes will undergo Bonferroni correction for multiple hypothesis-testing. Other pre-specified and post-hoc analyses are considered exploratory.

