6.2 Secondary outcomes

6.2.1. Proportion meeting LDL-C targets

The proportion of participants meeting individualized clinically significant LDL-C targets (<100mg/dL for primary prevention and <70 mg/dL for secondary prevention) will be determined at 6 months, using the LDL-C values as described for the primary outcome in Section 6.1.

Secondary prevention will be defined as any patient with any of the following:

Pre-existing atherosclerotic disease (ASCVD): acute coronary syndrome in the prior 12 months, history of myocardial infarction, history of ischemic stroke, symptomatic peripheral artery disease including aneurysm, all of atherosclerotic origin.

Presence of any ASCVD risk factors: age ≥ 65 years; prior percutaneous coronary intervention; prior coronary artery bypass graft; other evidence of coronary artery disease; diabetes mellitus; hypertension; chronic kidney disease; current smoking; congestive heart failure; family history of premature ASCVD; elevated coronary artery calcium score, Lp(a), or apoB; or ankle-brachial index < 0.9 .

All other participants will be considered eligible for primary prevention.

The primary or secondary prevention status of each participant will be determined by clinician review of participant medical records through the end-of-study date. The clinician reviewer(s) will be blinded to randomization status. For each participant deemed eligible for secondary prevention, the clinician will record the reason(s) for eligibility in a study database.

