6.2.2. Intensification of pharmacotherapy

The proportion of participants with an intensification of lipid-lowering pharmacotherapy will be determined from baseline and end-of-study prescription data, obtained from the CDW, medical record review, and patient surveys. Intensification of pharmacotherapy at 6-months will be a composite outcome including prescription of new monotherapy, dose escalation of existing pharmacotherapy, or addition of one or more medications to existing pharmacotherapy compared to baseline pharmacotherapy status.

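### The 80% power behind the enrollment of 244 is at alpha 0.05, but the SAP's Bonferroni rule for secondary outcomes implies a stricter level, at which power is about 71% on the same assumptions

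*SAP*

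**What the plan says.** **Sizing.** Section 3.2 calls the proportion meeting LDL-C targets an important secondary outcome and states: "To have 80% power to detect a between-arm difference of 20% of participants meeting this LDL-C target at alpha=0.05, up to 194 total participants". That is 97 per arm. It continues: "To account for up to 20% loss to follow-up, a total of 244 participants (122 per arm) are needed". The primary-outcome calculation in the same section stops at 180, so the target of 244 comes from this secondary outcome alone.

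**Test level.** Section 5.4 tests the primary outcome at 0.05. For the rest, it says that *P* "values reported as significant for secondary outcomes will undergo Bonferroni correction for multiple hypothesis-testing". It then adds: "Other pre-specified and post-hoc analyses are considered exploratory". It gives neither the number of tests in the correction nor the resulting level.

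**Which outcomes are secondary.** Section 6.2 has two entries. Section 6.2.1 is "The proportion of participants meeting individualized clinically significant LDL-C targets". Section 6.2.2 reads: "The proportion of participants with an intensification of lipid-lowering pharmacotherapy will be determined from baseline and end-of-study prescription data". Section 2.2 draws the line less clearly: "Secondary and exploratory objectives include an assessment of the difference in the proportions of participants reaching LDL-C targets between arms", followed in the same sentence by the other objectives.

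**Planning rate.** Section 3.2 reports that "only 175/322 (46%) MVP participants with a potentially pathogenic LDLR variant had a most recent LDL-C <100mg/dL".

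**The concern.** The calculation that fixes enrollment assumes a test level that the SAP's own multiplicity rule does not use for this outcome. Section 3.2 makes no allowance for the correction and does not say that its 80% is power before adjustment. A reader could therefore take a non-significant result on LDL-C targets as coming from a test with 80% power when, on the SAP's own rates and loss allowance, it had less.

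Leaving the family unnamed is a weakness in itself: the significance threshold for the secondary outcomes is not fixed before the data are seen.

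Three smaller faults sit in the same section:

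- The count and the percentage in the preparatory rate disagree.
- The planning rate and the table use <100 mg/dL for everyone, whereas the endpoint in Section 6.2.1 is <100 or <70 mg/dL by prevention status.
- The table is titled as the proportion below 100 mg/dL, yet all four rows put the lower proportion under Immediate Results.

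**Working it through.** **Inputs.** From Section 3.2: 80% power, a 20-point difference, alpha 0.05, rows 10/30, 20/40, 30/50 and 40/60, and 20% loss. From Section 3.3: 1:1 allocation. From Section 5.4: two-sided reporting and Bonferroni for secondary outcomes. From Section 7.3.1: Z-test or chi-squared test. Inferred: a family of two (Section 6.2), so 0.05/2 = 0.025.

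**Formulas** (pooled two-proportion normal approximation, with p̄ the mean of p1 and p2):

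- n per arm = [z(1−α/2)·√(2p̄(1−p̄)) + z(0.80)·√(p1(1−p1)+p2(1−p2))]² / (p1−p2)²
- power = Φ{ [|p1−p2|·√n − z(1−α/2)·√(2p̄(1−p̄))] / √(p1(1−p1)+p2(1−p2)) }

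**Reproducing the SAP at alpha 0.05, 40/60.** n = (1.960×0.7071 + 0.8416×0.6928)²/0.04 = (1.3859 + 0.5831)²/0.04 = 96.9, so 97 per arm and 194 in total. For loss, 97/0.8 = 121.25, so 122 per arm and 244 in total. Both match. The four rows come out at 124, 164, 186 and 194 against the stated 124, 162, 186 and 194; the 2-patient gap in the second row is rounding (81.2 per arm).

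**Same row at 0.025.** z = 2.2414, and 2.2414×0.7071 = 1.5849.

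- 97 per arm: (0.2×√97 − 1.5849)/0.6928 = (1.9698 − 1.5849)/0.6928 = 0.5555, power 71.1%.
- 122 per arm: (2.2091 − 1.5849)/0.6928 = 0.9009, power 81.6%.

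Exact binomial power of the same test is 71.7% and 81.7%.

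**All rows:**

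| Rates | 0.05, 97 per arm | 0.025, 97 per arm (20% loss) | 0.025, 122 per arm (no loss) |
|---|---|---|---|
| 40/60 | 80.0% | 71.1% | 81.6% |
| 30/50 | 81.7% | 73.1% | 83.3% |
| 20/40 | 86.6% | 79.3% | 88.4% |
| 10/30 | 94.2% | 90.0% | 95.7% |

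At 10% loss (122×0.9 = 109.8 per arm), 40/60 gives 77.0%.

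**If the family is larger.** Any Bonferroni family of two or more gives 0.025 or less. With three tests (0.05/3 = 0.0167), 40/60 gives 65.5% at 97 per arm and 77.2% at 122.

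**The preparatory rate.** 175/322 = 54.3%. The complement is 322 − 175 = 147, and 147/322 = 45.7%, so the printed 46% may be the proportion not below 100 mg/dL. A 20-point gain at 0.025 from either reading gives:

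- 46/66: 71.8% at 97 per arm, 82.2% at 122.
- 54.3/74.3: 75.2% and 85.1%.

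At 0.05 these need 96 and 89 per arm (192 and 178 in total), both under 194. The 40/60 pair is symmetric about 50% and so needs the largest sample for any 20-point difference. Swapping the arm headings leaves two-sided power unchanged. None of the smaller faults therefore raises 194.

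**The case against.** The strongest reply is that nothing was miscalculated. Section 3.2 prints alpha 0.05 next to the 80%, sizing a secondary outcome before multiplicity adjustment is common, and the SAP nowhere promises 80% after Bonferroni. The 0.025 is inferred. The loss allowance is a ceiling: with complete follow-up every row exceeds 80% at 0.025. Sections 5.5 and 6.1 permit imputation and chart or carried-forward values, and the analysis is by intention to treat, so the analysed number may lie nearer 122 than 97. Section 6.2.1 defines secondary prevention broadly; if many participants fall under <70 mg/dL, attainment may be low enough for the 20/40 or 10/30 rows to apply, with 79% and 90% even at full loss. Type I error is controlled once the family is named.

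Most of this is true and limits the size of the point. The sum is correct at its stated level, and the shortfall belongs to the higher-loss, mid-range-rate cases. The point still stands, because 20% loss and the 40/60 row are the SAP's own basis for 194 and 244, and 0.025 is the mildest level that any Bonferroni family of two or more gives. Carried-forward and imputed values may also dilute the difference, so counting them as full observations is optimistic. The SAP gives no mix of prevention status from which to choose a row.

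**Conclusion.** The concern holds. On the assumptions from which Section 3.2 derives 194 and 244 (40% versus 60%, full 20% loss), power at the level implied by Section 5.4 is about 71%, roughly 9 points below the stated 80%. Over the SAP's four rows it is 71% to 90% at full loss and 82% to 96% with none. This rests on a Bonferroni family of the two outcomes in Section 6.2; a larger family lowers every figure.

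The consequence is confined to the stated power of one secondary outcome and to an unnamed family. The primary outcome is tested at 0.05 without correction and is not affected; nothing here bears on whether 180 or 244 is adequate for it. The preparatory percentage is wrong for its printed count, and the threshold and table headings need reconciling, but none of these changes the 194.

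**What to change.** **Section 3.2, power.** State that, before multiplicity adjustment (alpha 0.05), 97 evaluable per arm gives 80% power for 40% versus 60%. Add that at 0.025 (Bonferroni, two secondary outcomes) power with 97 per arm is 71% (40/60), 73% (30/50), 79% (20/40) and 90% (10/30), and with 122 per arm (no loss) 82%, 83%, 88% and 96%.

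**Section 5.4.** State that the Bonferroni family is the two secondary outcomes in Section 6.2, at 0.025 each. If another family is meant, name it and recompute the figures above.

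**Section 3.2, smaller corrections.** Check the source data and correct whichever of 175/322 and 46% is wrong. Say that the planning rate and table use <100 mg/dL for everyone, while the endpoint uses <100 or <70 mg/dL by prevention status. Reconcile the table's title with its arm headings.

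**Cost.** A few sentences in two sections and a check of preparatory data already held. No change to enrollment is asked for on this ground. The one downside is that the stated power for this outcome becomes less favourable.
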